Serum digoxin concentrations, BUN, Creatinine, CBC, Electrolytes (Na, K) and ECGs will be obtained weekly. pregnancy testing for female participants of childbearing potential and a baseline screening to determine if you are eligible for this study. Peripheral blood (25ml) in EDTA tubes (purple top) will be obtained at 0, 1, 2, 3 weeks after starting digoxin, with written consent and in accordance with the guidelines of Yale University ethics committee. PMN and monocytes will be isolated using PolymorphPrep (Axis-Shield) according to standard procedure, and purity will be determined by flowcytometric analysis. Spontaneous ROS of PMNs will be measured by culturing neutrophils with CM-H2DCFDA for 30 minutes, washing, followed by kinetic analysis of intracellular ROS with fluorescent plate reader. Neutrophils up-regulate ROS spontaneously in culture, and for each sample the untreated aliquot will be the control for the digoxin treated aliquot. Monocytes will be stimulated LPS (100ng/ml) for 3 hrs after which cDNA will be prepared and qPCR conducted for IL-1B, TNF- α and IL-6. cDNA and supernatant will be stored for further analysis based on initial results.

These initial numbers are based the use of similar assays in the preliminary data. We will obtain additional assistance from [name] Professor of Biostatistics at the University of Massachusetts, who will 1) review of study design, including sample size and specimen utilization; 2) develop an appropriate data management system to provide data capture and edit capabilities; 3) develop appropriate statistical analysis, quality assurance, and quality control plans; 4) conduct the statistical analysis and provide material for presentation/publication; and 5) provide resources to assure reproducible research. Please see letter of support.

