F) Pregnancy: *The chance of a female subject to become pregnant on a 4-week study is very less, if in case this does happen they will be asked to stop the drug and withdraw from the study immediately. We do not intend to follow the pregnancy and birth outcome.*

Drug preparation: Digoxin is commercially available as a 0.05mg/ml elixir (Boehringer Ingelheim). The appropriate dosing of digoxin and control will be prepared with the help of the Yale Center for Clinical Investigation (YCCI) as detailed in the facilities and resources. Stopping criteria: Subjects will be removed from the study if any serum digoxin level is above 0.8ng/ml, or if there are any abnormalities in blood tests or ECGs. Data from these subjects will not be used in the analysis. Analysis, expected outcome and alternative approaches: It is expected that there will not be a significant difference in the neutrophil ROS and monocyte qPCR results in control group A between the four time points. It is expected that for group B and C, both neutrophil ROS and monocyte qPCR levels will be lower at time points 1, 2, 3 weeks as compared to time 0, and as compared to all time points of group A. It is not clear if in group D time points of week 1, 2, and 3 will be any different from time point 0. For the time points where significant differences are found we will perform additional luminex assay with the supernatant using the luminex five plex panel (GM-CSF, IL-1B, IL-6, IL-8, TNF- α). There will also be an analysis of the production of ROS and qPCR levels in relation to serum digoxin levels at the time that the analysis samples were obtained. The combinations of these analysis will establish that digoxin taken orally is effective in reducing inflammatory responses, and will also provide information on dose response for oral dosing as well as serum concentrations.

5. Genetic Testing N/A

A. Describe

- i. the types of future research to be conducted using the materials, specifying if immortalization of cell lines, whole exome or genome sequencing, genome wide association studies, or animal studies are planned *Write here*
- ii. the plan for the collection of material or the conditions under which material will be received *Write here*
- iii. the types of information about the donor/individual contributors that will be entered into a database *Write here*
- iv. the methods to uphold confidentiality *Write here*

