The principal investigator (*[name]*) will conduct a review of all adverse events upon completion of every study subject. The principal investigator will evaluate the frequency and severity of the adverse events and determine if modifications to the protocol or consent form are required.

Please note: For any study that may be considered high risk, the IRB will be more focused on the safety requirements for the study and a DSMB will likely be required.

- d. For multi-site studies for which the Yale PI serves as the lead investigator:N/A
 - i. How will adverse events and unanticipated problems involving risks to subjects or others be reported, reviewed and managed? *Write here*
 - ii. What provisions are in place for management of interim results? *Write here*
 - iii. What will the multi-site process be for protocol modifications? *Write here*

13. Statistical Considerations: Describe the statistical analyses that support the study design.

Primary analyses of the biochemical measures will be conducted using mixed effects models to account for the correlation among the biochemical measures obtained from repeated blood draws on the same participant. The models will include digoxin dose (3 mcg/kg/day, 0.15 mcg/kg/day, none/placebo), time on study (weeks 0, 1, 2, and 3), and relevant patient characteristics (i.e., age, gender). A random intercept will be included so that each participant will have their own starting point and time will be a categorical predictor to better model a potential curvilinear relationship between time on study and biochemical levels without assuming a linear slope. Because treatment group is a three-level variable, we will first conduct a Type III multi-degree of freedom test to determine if any difference exists among the three groups and, if that is significant, conduct all pairwise comparisons to determine where the difference is. Because these tests are not independent, we will apply a Bonferroni correction to the critical p-value to reduce the possibility of a Type I error by chance alone. In this case, the critical p-value will be set at $0.05/3 = 0.017$ so that any p-value less than 0.017 will be declared statistically significant.

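### Four biochemical outcomes share primary status, but the 0.017 level corrects only for the three group pairs, and the time contrast differs between sections

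*Combined protocol and SAP*

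**What the plan says.** Section I, item 13 (Statistical Considerations) opens: "Primary analyses of the biochemical measures will be conducted using mixed effects models". It neither lists nor ranks the measures. For treatment group it plans a Type III test across the three groups and, "if that is significant, conduct all pairwise comparisons to determine where the difference is". It then states "we will apply a Bonferroni correction to the critical p-value to reduce the possibility of a Type I error by chance alone", sets the level at 0.05/3 = 0.017, and adds that "any p-value less than 0.017 will be declared statistically significant". No separate level is given for the overall test.

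The model terms listed are dose, time (weeks 0, 1, 2 and 3), age and gender, with a random intercept; "time will be a categorical predictor". No dose-by-time term is listed.

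The measures themselves are in Section I, item 4 (Research Plan), part A: spontaneous neutrophil ROS, and LPS-stimulated monocytes, from which "cDNA will be prepared and qPCR conducted for IL-1B", TNF-alpha and IL-6.

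The paragraph of item 4 on analysis and expected outcome says "It is expected that for group B and C, both neutrophil ROS and monocyte qPCR levels will be lower" at weeks 1, 2 and 3, both against time 0 and against placebo. It continues: "For the time points where significant differences are found we will perform additional luminex assay". It concludes that the analyses taken together will establish that oral digoxin works, without saying how many outcomes must be positive.

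**The concern.** The plan adopts a formal threshold in order to limit chance findings, but the threshold counts only one source of multiplicity, the three group pairs. Four outcomes carry the conclusion, and one positive outcome out of four could be presented as success.

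The two sections also describe different tests over time. Item 13, read literally, gives one dose effect averaged over all four visits, including the pre-treatment one. Item 4 acts on differences at individual weeks. With 15 per group, what is reported as a digoxin effect could depend on which outcome and which week are emphasised after the data are seen.

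**Working it through.** **Inputs from the documents.** Three groups of 15 (item 4, part A). Four outcomes (item 4, part A). Three group pairs, tested only after a significant overall test (item 13). Pairwise level 0.017 (item 13).

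**Assumptions.** The documents give no correlation between outcomes, so 0, 0.5 and 0.9 are used. The overall test is taken at 0.05. That is the likelier reading, because 0.017 is derived from the number of pairs and the analogous safety analysis in item 13 stays at 0.05. The words "any p-value less than 0.017 will be declared statistically significant" could cover the overall test too, so 0.017 is also shown. Outcomes are taken as normal with equal variance and one contrast per pair.

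**1. The plan's own figure.** 0.05/3 = 0.01667, which rounds to 0.017. Three independent tests at that level give 1 - (1 - 0.017)^3 = 5.0%. The figure is right for three pairs on one outcome.

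**2. Chance of a false claim with all groups equal.** Simulation, 200,000 trials per setting: for each outcome an F test on 2 and 42 degrees of freedom, then three two-sided pooled-variance t tests.

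| Rule and event counted | Correlation 0 | 0.5 | 0.9 |
|---|---|---|---|
| Overall test 0.05, pairs 0.017: any false pair, either direction, four outcomes | 16% | 14% | 8% |
| Overall test and pairs both 0.017: same event | 7% | 6% | 4% |
| Overall test 0.05, pairs 0.017: false reduction against placebo on any of four outcomes | 6% | 5% | 3% |
| Same levels: false reduction on ROS and on at least one cytokine | 0.1% | 0.5% | 1.2% |

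For a single outcome at 0.05 then 0.017, any false pair occurs in 4.2% of trials and a false reduction against placebo in 1.5 to 1.6%. As a check on the first row, four independent outcomes give 1 - (1 - 0.042)^4 = 15.8%.

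**3. The time contrast.** With balanced visits and no dose-by-time term, the dose effect in item 13 is the difference in four-visit means. If a dose shifts the outcome by d at weeks 1, 2 and 3 and by nothing at week 0, that contrast estimates (0 + d + d + d)/4 = 0.75d. So week 0 dilutes it by a quarter, and it does not answer item 4's weekly question.

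**4. Weekly testing.** The table contains no multiplicity over weeks. If pairs were tested at 0.017 on change from baseline at each of weeks 1 to 3 with no overall test first, one outcome alone would give about 11 to 12% (assumed within-subject correlation 0.5). With a 0.05 test of the 6-degree-of-freedom interaction first, four outcomes give about 14/13/8%, close to the first row.

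**The case against.** **The headline figure is not the risk of the intended conclusion.** It counts every pair in either direction, including dose against dose and false increases. A reader might infer a 16% chance of wrongly declaring that digoxin reduces inflammation. The documents do not support that: the matching figure is about 6/5/3%. If neutrophil ROS and at least one cytokine must both fall, which is one reading of item 4, it is about 1% or less. This objection stands and limits the point. It does not remove it, because 6/5/3% is still two to four times the single-outcome figure and the plan never states the joint rule.

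**Zero correlation is the extreme case.** Three outcomes are transcripts from the same stimulated monocytes, so some correlation is plausible. This stands; the upper end of each range should not be quoted alone.

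**A reader might say that no time contrast exists.** That goes too far. Item 13 implies one; it conflicts with item 4 and includes week 0.

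**A reader might argue that 0.017 is needlessly strict after an overall test and should become 0.05.** That would hold only for one outcome, one contrast per pair and exactly three groups. With pairs tested weekly and one dose active it gives 10 to 14% error, and with four groups 11 to 12%. The plan is not yet settled on either condition.

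**Primary may describe the method rather than rank endpoints, and this is a pilot** with a biostatistician assigned to develop the analysis plan. Both are fair and bear on severity. But item 13 sets a significance rule, and item 4 expects the analyses to establish an effect.

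**Conclusion.** The point holds in limited form. The 0.017 level does its job for one outcome (4.2%) but not across the four that the plan treats as primary: about 16/14/8% for any false pairwise claim with a 0.05 overall test, or 7/6/4% if that test is also at 0.017. The 4% at correlation 0.9 is the one value below 5%. For a false reduction against placebo the figures are 6/5/3%, against 1.5 to 1.6% for one outcome. All rest on assumed correlations, all groups equal, and a count of four taken from item 4.

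That no outcome is ranked, and that items 13 and 4 imply different time contrasts, can be read directly from the text and needs no assumption. This should be corrected, but it does not invalidate the design.

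**What to change.** Before outcome data are analysed, amend item 13 and align item 4 with it:

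- **Outcome.** Name one primary outcome, or state a rule such as ROS plus at least one cytokine.
- **Contrast.** Name one post-baseline between-group contrast per pair, for example the weeks 1 to 3 average with week 0 as baseline.
- **Levels.** State 0.05 for the overall test on that contrast and keep 0.017 for the three pairs (about 4.2% error for one outcome). Do not relax the pairs to 0.05.
- **Everything else.** Label the other outcomes, the week-by-week tests, the within-group comparisons with time 0 and the serum-level analysis secondary or exploratory.
- **Groups.** Reconcile item 4's mention of a group D, and the 60 subjects in Section I, item 6 and Section III, item 1, with three groups of 15. The divisor 3 assumes three groups.

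If all four outcomes stay co-primary, with three groups and one contrast per pair, two options hold 5%. One is 0.0125 (0.05/4) for both the overall test and the pairs, giving about 4.9/4.4/2.8%. The other is a 0.05 overall test with pairs at 0.05/12 = 0.0042, giving about 4.4/4.0/2.4%. In the second, a significant overall test alone must not be reported as a finding, since at least one occurs by chance in about 18/16/10% of trials.

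**Cost.** Wording only: no added subjects, visits or assays. One outcome and one contrast must be chosen in advance, and the others lose primary status. Keeping four co-primaries costs power instead. For an assumed difference of 1 SD of the contrast, with the other dose equal to placebo, power for one named pair on one outcome is about 60% at 0.05 then 0.017, 49% at 0.0125 throughout, and 40% at 0.05 then 0.0042.

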
regulate expression of numerous genes. Interestingly, digoxin does not alter PKM2 kinase activity but suppresses PKM2 dependent transcriptional activity. This area is significant because sterile inflammation (SI) is the central pathological process in AH. Our results identify PKM2 as a key molecule in liver sterile inflammation which can be therapeutically targeted. The identification of digoxin as a PKM2 binder, which leads to critical anti-inflammatory effects, provides a novel opportunity to reduce liver inflammation in AH. We have further identified a unique molecular profile from a pilot aptamer-proteomic screen which will be expanded to the whole InTeam cohort to provide predictive markers for severe AH.

4. **Research Plan:** Summarize the study design and research procedures using non-technical language that can be readily understood by someone outside the discipline. **Be sure to distinguish between standard of care vs. research procedures when applicable, and include any flowcharts of visits specifying their individual times and lengths.** Describe the setting in which the research will take place.

Test if administering digoxin orally to healthy subjects results in a reduction in innate immune inflammatory responses in the peripheral blood.

We need to obtain peripheral blood lymphocytes from healthy subjects on different doses of digoxin to test if digoxin has an effect on the immune response of PBLs.

A) There will be three study groups.

Groups:

A: Placebo n=15

B: Digoxin 3 mcg/Kg/day n=15

C: Digoxin 0.15 mcg/Kg/day n=15

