B) The data management system will be set up in the University of Massachusetts Medical School secure REDCap environment, which is used for all of the pilot studies funded by NIAAA as part of the AlcHepNet Research Network. This HIPAA-compliant, 21 CFR Part 11 compliant environment is accessible only by medical school staff and collaborating clinical sites of the AlcHepNet who are assigned an account in this environment by UMMS IT with approval by the UMMS IRB. The system will be programmed for a single entry with validation rules at the time of entry and additional checking conducted after the data have been submitted to the main data base. These edits will check for validity, consistency, and normal range values. Edit queries will be generated and resolved by clinic staff with corrections posted to the database through the REDCap system, which enforces an audit trail for all changes. The study database will be stored in REDCap within the secure environment to protect any PHI/PII data

that are collected as part of the study. We will strive to minimize collection of such data and REDCap will be programmed to segregate that data from the study data so that exports for analysis will be deidentified. Data will be exported from REDCap for import into the latest version of SAS (SAS Institute, Cary, NC) or other statistical software for all analysis.

C-E) All reports and analyses will be generated from these files. Data files (and accompanying programs) that are used for reports, presentations, or publication will be archived as required past the end of the study. REDCap will also have the audit trail capability enabled for tracing any data modifications. Data from laboratories can be uploaded directly into REDCap for storage. The REDCap system will be programmed and maintained by study staff at the U Mass Medical School AlcHepNet Data Coordinating Center while data entry will be performed by study staff at the local site.

The sample size for this pilot study was based on results from in vitro experiments, where differences in as few as 5 participants were seen to be significantly different. Given the inherent variability in the absorption of digoxin in humans, a sample size of 15 was determined to be reasonable to provide a reasonable distribution of results from repeated measures of participants at the differing digoxin dose levels.

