Adherence analysis will be ascertained using pill counts for each participant at the weekly visits. For safety analyses, we will record any adverse events, both serious (SAE) and not, described by the participant at each weekly visit. Each AE will include a description of the AE/SAE, relatedness to digoxin, and resolution. These will be summarized by treatment group and, if there are three or more participants in any one group with a specific AE/SAE, we will conduct a statistical test (Likelihood Ratio Chi-Square) to determine any statistically significant difference among the treatment groups using the analogous approach as above to first test for any difference in the incidence of AE/SAE among the three treatment groups followed by conducting the three pairwise comparisons, again using the Likelihood Ratio Chi-Square. Because this is a safety analysis, the critical p-value is left at 0.05 for all comparisons to avoid increasing the probability of a Type II error.

SECTION II: RESEARCH INVOLVING DRUGS, BIOLOGICS, RADIOTRACERS, PLACEBOS AND DEVICES

If this section (or one of its parts, A or B) is not applicable, check off N/A and delete the rest of the section.

A. RADIOTRACERS

N/A

1. Name of the radiotracer: *Write here*
2. Is the radiotracer FDA approved? YES NO

If NO, an FDA issued IND is required for the investigational use unless RDRC assumes oversight.

3. Check one: IND# *Write here* or RDRC oversight (RDRC approval will be required prior to use)
4. **Background Information:** Provide a description of previous human use, known risks, and data addressing dosage(s), interval(s), route(s) of administration, and any other factors that might influence risks. If this is the first time this radiotracer is being administered to humans, include relevant data on animal models.
Write here
4. **Source:** Identify the source of the radiotracer to be used. *Write here*
5. **Storage, Preparation and Use:** Describe the method of storage, preparation, stability information, method of sterilization and method of testing sterility and pyrogenicity.
Write here

B. DRUGS/BIOLOGICS

N/A

1. If an **exemption from IND filing requirements** is sought for a clinical investigation of a drug product that is lawfully marketed in the United States, review the following categories and complete the category that applies (and delete the inapplicable categories):

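### For one outcome and one overall three-group effect, the significant overall test already protects the three pairwise tests, so the added 0.05/3 rule costs power for no needed error control

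*Combined protocol and SAP*

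**What the plan says.** The Research Plan (Section I, item 4) states "There will be three study groups": placebo, digoxin 3 mcg/kg/day and digoxin 0.15 mcg/kg/day, with 15 in each. On numbers it says only that "a sample size of 15 was determined to be reasonable"; it gives no effect size, SD or power.

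Item 13 sets the primary analysis as a mixed model with dose, categorical week and subject characteristics. For the dose factor, "we will first conduct a Type III multi-degree of freedom test to determine if any difference exists among the three groups". The pairwise step depends on that result: "if that is significant, conduct all pairwise comparisons to determine where the difference is". The plan then tightens the pairwise level, giving the dependence among the tests as its reason: "we will apply a Bonferroni correction to the critical p-value to reduce the possibility of a Type I error by chance alone". The critical value becomes 0.05/3, and "any p-value less than 0.017 will be declared statistically significant".

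The safety paragraph of the same item uses the same two-step scheme for adverse events, but there "the critical p-value is left at 0.05 for all comparisons to avoid increasing the probability of a Type II error".

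**The concern.** Item 13 guards the same three comparisons twice: once by requiring a significant overall test, and again by dividing the pairwise level by three. With three groups the first guard is sufficient for a single group effect. The stated reason for the second, that the tests are not independent, does not call for it: Bonferroni is valid under dependence, but dependence does not make it necessary.

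What is at stake is power. The dose-placebo comparisons carry the study's conclusion on 15 subjects per group, and subjects removed under the stopping criteria are dropped from the analysis. The double guard also allows a significant overall test with no pair declared different, which leaves an awkward result to report.

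**Working it through.** **The plan's own figure.** 0.05/3 = 0.01667, which rounds to the stated 0.017. There is no power figure to reproduce.

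**Inputs.** From the documents: three groups, 15 per group, overall test first, three pairs, pairwise level 0.05/3. Assumed because the documents are silent: overall test at 0.05, two-sided pairwise tests, all 15 per group analysable, and standardized difference d in SDs of the participant-level summary. With balanced data the group test in a random-intercept model is the one-way test on participant means, with 45 − 3 = 42 residual df before covariates.

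**Why the overall test is enough.** Call the pairwise nulls AB, AC and BC. Any two of them together imply A = B = C. So only two cases allow a false pairwise claim:

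1. All groups are equal. A false claim needs a significant overall test, which has probability 0.05.
2. Exactly one pair is equal. A false claim needs that one test to reject, which has probability at most 0.05.

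**Familywise error, simulated (one outcome, one group effect).**

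| True state | Pairs at 0.05 | Pairs at 0.05/3 |
|---|---|---|
| All groups equal | 5.0% | 4.2% |
| One dose very different, the other equal to placebo | 5.0% | 1.7% |

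Without the overall test, pairs at 0.05 would give about 12% when all groups are equal. The overall test removes that excess.

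**Power of one active dose against placebo, overall test at 0.05, both doses equally effective.**

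| d | Pairs at 0.05 | Pairs at 0.05/3 | Cost (points) |
|---|---|---|---|
| 0.5 | 19.2% | 14.1% | 5 |
| 0.7 | 37.9% | 29.2% | 9 |
| 0.8 | 49.0% | 38.8% | 10 |
| 1.0 | 70.8% | 59.8% | 11 |
| 1.2 | 86.9% | 78.2% | 9 |
| 1.5 | 97.6% | 94.1% | 3 |
| 1.8 | 99.7% | 99.1% | under 1 |

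The active dose gives the same figures to within simulation error when the other dose is inactive.

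**Graded effect.** If the low dose has half the high-dose effect and d = 1.0 for the high dose, the high dose goes from 64.2% to 59.5% (5 points) and the low dose from 25.1% to 14.2% (11 points). The low-dose cost reaches about 18 points at larger d.

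**Fewer analysable subjects.** With 12 per group and equal effects, the cost is 7-11 points for d = 0.7-1.3.

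**Significant overall test with no pair declared.** This occurs in about 2-4% of trials for d = 0.8-1.2 under the plan. It cannot occur with balanced groups, pooled-variance tests and pairs at 0.05. The overall test is significant when F exceeds 3.22 (2 and 42 df). The largest pairwise t² is then at least 1.5 × 3.22 = 4.83, so |t| is at least 2.20. That is above the 0.05 limit of 2.02 but can fall below the 0.05/3 limit of 2.49.

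**The case against.** **Weekly comparisons.** The strongest objection is that the 0.017 level may do real work. Item 13 names no dose-by-time term and tests the three groups as one factor, so a single overall effect is its natural reading. The analysis paragraph of item 4, however, states expectations week by week and makes further assays depend on the time points that show differences. If the pairs are tested at each of weeks 1-3 after a single overall test, closure fails. With one dose very effective, familywise error is then 0.11-0.14 at 0.05 and 0.04-0.05 at 0.05/3. This stands. A reader might infer that the Bonferroni step is pointless under every reading; the documents do not settle the contrast, so they do not support that.

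**Size.** A reader might also infer a fixed loss of about ten points on each dose-placebo comparison. The documents give no effect size or SD. The loss shrinks outside d = 0.7-1.2 and differs between doses if the effect is graded. An inactive dose has no power to lose.

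**Level of the overall test.** The sentence setting 0.017 could be read as covering the overall test too. The cost against 0.05 throughout would then be about 13-18 points for d = 0.7-1.2 with equal effects. This ambiguity stands.

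**Several outcomes.** Item 4 lists four measures (neutrophil ROS, IL-1B, TNF-α, IL-6) and no correction across them is given. Treating them as independent, which overstates the effect if they are positively correlated: with one pair truly equal and the other dose very different, 1 − (1 − 0.017)^4 = 6.6% under the plan and 1 − (1 − 0.05)^4 = 18.5% after the change. With all groups equal, 1 − (1 − 0.042)^4 = 15.8% and 18.5%. The stricter rule therefore gives some incidental cover across outcomes, little of it when nothing works.

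**Deliberate choice.** The safety paragraph shows that the authors weighed Type II error and chose to be stricter for the biochemical measures. Different levels for efficacy and safety are not a contradiction, and a conservative rule in a pilot is defensible.

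**Conclusion.** The point holds for one outcome and one overall effect across exactly three groups. There, an overall test at 0.05 followed by pairs at 0.05 controls familywise error at 0.05, and the 0.05/3 rule is redundant.

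Under the stated assumptions the cost is about 9-11 points for an active dose at d = 0.7-1.2, about 5 at d = 0.5 and about 3 at d = 1.5. It splits as 5 and 11 points between high and low dose for a half-effect low dose at d = 1.0.

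The argument needs exactly three groups. Items 4 and 13 say three, giving 3 × 15 = 45, although item 4 also mentions a group D and the enrolment target is 60. With a fourth group this closure would not hold.

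Nothing here makes the plan invalid: its rule is conservative. This is a cheap improvement in efficiency.

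**What to change.** Replace the 0.05/3 sentences in Section I, item 13 with wording such as:

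> For each outcome, the overall Type III test of the three-group effect is done at the 0.05 level. If it is significant, the three pairwise comparisons of that same overall group effect are each tested two-sided at 0.05; with three groups this is a closed procedure. Comparisons at individual weeks are not covered by this overall test and are either exploratory or separately adjusted.

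This also states the level of the overall test and the contrast tested, both now left open. If a smaller level is later set for each outcome, use it for both the overall test and the pairs.

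The cost is a few sentences of text and no extra subjects. There are two small downsides. Unadjusted 95% intervals for the pairs are not simultaneous and should be labelled so. The incidental conservatism across the several uncorrected outcomes is lost, so multiplicity across outcomes should be dealt with openly or the outcomes described as exploratory.
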